9.3.4. Outcomes

9.3.4.1. Congenital malformations

The study will define and code congenital malformations using the criteria specified by the CDC MACDP and EUROCAT.^{40,41} A malformation may be described and classified by severity (eg, major malformation), by origin (eg, genetic, environmental exposure), and by organ system (eg, urogenital system or malformations known as congenital heart defects [CHD]). An MCM will be defined as any major structural or chromosomal defect detected in live-born infants, stillbirths/fetal losses ≥ 20 gestational weeks, and elective terminations of any gestational age.⁴⁰ This definition is consistent with, but not restricted to, the CDC MACDP and EUROCAT definitions.

To avoid misattribution of the malformation to the medication, MCMs not associated with medication exposure, such as chromosomal abnormalities, genetic syndromes, prematurity-related conditions in infants born at < 36 gestational weeks (eg, patent ductus arteriosus, patent foramen ovale, inguinal hernias, or undescended testes), and positional effects (eg, hip dislocation due to breech position or abnormal skull shape due to crowding by multiple fetuses), will not be considered MCMs in the statistical analyses comparing MCM prevalence between the internal cohorts.⁴² Given that the registry will also use the CDC's MACDP and EUROCAT as external comparators, the registry will include cases of MCMs not associated with medication exposure in the prevalence calculations for this comparison.

Transient malformations in term infants, whether occurring alone or with other malformations, will be reported in the study, as certain transient malformations may be associated with maternal medication exposure in pregnancy and can vary by age of detection and/or age of resolution (eg, CHDs).⁴³ Lastly, the MACDP only includes minor malformations if they occur in the presence of an MCM. However, as stated in the objectives, major and minor malformations are of interest for this study and both will be reported.

Live-born infants with only positional defects (malformations), infectious conditions, or with biochemical abnormalities will be classified and reported separately. The CDC MACDP has different objectives and reporting needs than this project, so a thoughtful adaptation of their guidelines is appropriate.

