9.5.2. Full study

The full study will aim to prospectively enroll a minimum of 390 women with migraine who were exposed to rimegepant during pregnancy or just prior to pregnancy (up to 3 days prior to conception), as well as an internal comparison cohort consisting of 390 women with migraine who were not exposed to rimegepant during pregnancy or just prior to pregnancy (up to 5 product half-lives prior to conception). The target sample size for the registry is based on the primary outcome, MCM, which is also the outcome with the most restrictive denominators and 1 of the lowest prevalence rates in the general population. If all are evaluable for potential MCMs (evaluable being those for whom pregnancy outcome and major/minor congenital malformation assessments are obtained), and assuming an approximate 3% overall population prevalence of MCM, ⁵⁴ at α =0.05, this sample size provides 80% power to detect a 2.5-fold increased risk for overall MCM. Most registry power calculations are performed for overall MCM to detect an increased risk between 2- and less than 3-fold.⁵⁵ A midpoint threshold of a 2.5-fold increased risk was selected for this study. Assumptions for study calculations are consistent with those applied in the retrospective pregnancy outcomes study (NDA 212728, postmarketing requirement 3799-7, Pfizer study C4951006 [formerly BHV3000-403]).

Prospective enrollment can occur only after pregnancy is recognized but while the pregnancy is ongoing. Therefore, early pregnancy losses will not be captured, and a live birth rate higher than that of the general population would be expected. Research shows that approximately 90% of pregnancies enrolled in pregnancy exposure registries result in a live birth.^{56,57} Assuming that 90% of prospectively enrolled pregnancies result in live births and 10% are lost to follow-up,⁵⁸ at α =0.05, the study sample of 390 prospectively enrolled pregnant women in each internal cohort would result in 316 evaluable participants per cohort. Therefore, the study would have 80% power to detect a 2.7-fold increased risk of overall MCM (Table 2).

PFIZER CONFIDENTIAL

Outcome	N per cohort	Reference rate	Relative risk detectable	Power ^b
МСМ	390	3% ^{54,55,59}	2.5	80.6%
МСМ	316 ^a	3% ^{54,55,59}	2.7	80%

Table 2.	Sample Size and Power Estimates for Primary	Outcome, MCM

MCM = major congenital malformation; reference rate = prevalence rate of outcome in general population for pregnant women of any age

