^a Assumes that 90% of prospectively enrolled pregnancies result in live births and 10% are lost to follow-up, resulting in 316 evaluable participants

^b Power calculations based on normal approximation, 2-tailed, α =0.05⁶⁰

Additionally, Table 3 shows that, without any adjustments for multiple comparisons, the proposed sample size (390 pregnant women) will afford the study >80% power to detect a 2.5-fold increase in all other outcomes except eclampsia, stillbirth, and TOPFA (for which the study will have <20% power to detect a 2.5-fold increase).

Table 3.	Power Calculations
----------	---------------------------

Outcome	Reference rate	Power estimate ^a
MCM ^{54,55,59}	3%	80.6%
Gestational diabetes ²⁹	6.9%	>99.0%
Gestational hypertension ⁶¹	6.5%	>99.0%
Pre-eclampsia ⁶²	3.40%	85.5%
Eclampsia ⁶¹	0.3%	2.7% ^b
SAB ⁶³	13.4%	>99.0%
Stillbirth ⁶⁴	0.596%	12.6% ^b
Elective termination ⁶⁵	18.6%	>99.0%
TOPFA ⁶⁶	0.4%	5.8% ^b
Preterm birth ²⁹	8.47%	>99.0%
SGA*	10.0%	>99.0%
Postnatal growth deficiency*	10.0%	>99.0%

MCM = major congenital malformation; reference rate = prevalence rate of outcome in general population for pregnant women of any age; SAB = spontaneous abortion; SGA = small for gestational age; TOPFA = termination of pregnancy for fetal anomaly.

*By Definition

^a Power calculations were conducted using nQuery and were based on normal approximation, 2-tailed, alpha 0.05.

^b Fisher's Exact test was used for power calculation.

PFIZER CONFIDENTIAL

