9.7.3.3. Calculation of outcome prevalence

Prevalence rates of the outcomes of interest will be calculated according to the conventions described in Table 4. In general, the prevalence of each outcome will be calculated by dividing the number of cases of the outcome by the appropriate denominator for that particular outcome, based on clinical knowledge and/or the methodology used by the external comparator. Prevalence is preferred over incidence when examining pregnancy outcomes, such as congenital malformations, because incidence cannot be reliably estimated given the complexities in the reproductive process.⁶⁷

For most outcomes, the main analysis population (denominator) will be the number of pregnant women with pregnancy outcome data, the number of live births, or the number of infants with follow-up data at the timepoint of interest, as appropriate; however, for some outcomes, the main analysis population (denominator) will be restricted based on certain relevant factors:

- For MCM, prevalence in the rimegepant-exposed cohort will be calculated among the subset of women who are exposed during the first trimester.
- For MCM, prevalence will be calculated among live births for the primary analysis, and a secondary analysis will be conducted among live births and fetal losses.
- For preterm birth, SGA, and postnatal growth deficiency, prevalence will be calculated among singleton live births due to the higher risk of these outcomes in twins and higher-order multiples.
- For live birth and infant outcomes (ie, preterm birth, SGA, postnatal growth deficiency, and infant developmental delay), prevalence will be calculated among live births/infants without MCMs.
- For postnatal growth deficiency, infants born preterm or SGA will be excluded from the main analysis population (denominator).
- For infant developmental delay, infants born preterm will be excluded from the main analysis population (denominator).
- For SAB and preterm birth, prevalence will be calculated among the subset of women who are enrolled in the registry prior to 20 and 37 gestational weeks, respectively.
- For some outcomes, prevalence will be calculated at multiple timepoints. For example, postnatal growth deficiency and infant developmental delay will be assessed at 2, 4, 6, and 12 months of

PFIZER CONFIDENTIAL

infant age. At each timepoint, prevalence will be calculated among infants with data available for the particular outcome at that timepoint.

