Comparison with external comparator (EUROCAT) ⁴⁴	TOPFA among women with pregnancy outcome data	Live births and stillbirths among women with pregnancy outcome data
Preterm birth		
Primary analysis between internal cohorts	Singleton preterm live births without MCMs among women with pregnancy outcome data who are enrolled (and exposed, if applicable) prior to 37 gestational weeks	Singleton live births without MCMs among women with pregnancy outcome data who are enrolled (and exposed, if applicable) prior to 37 gestational weeks
Comparison with external comparator (Pfizer Study C4951006)	Preterm live births among women with pregnancy outcome data who are	Live births among women with pregnancy outcome data who are

PFIZER CONFIDENTIAL

Outcome	Numerator	Denominator
	enrolled (and exposed, if applicable) prior to 37 gestational weeks	enrolled (and exposed, if applicable) prior to 37 gestational weeks
SGA		
Primary analysis between internal cohorts	Singleton live births without MCMs who are SGA based on weight/length/head circumference among women with pregnancy outcome data	Singleton live births without MCMs with weight/length/head circumference data among women with pregnancy outcome data
Comparison with external comparator (Pfizer Study C4951006)	Live births who are SGA based on weight among women with pregnancy outcome data	Live births among women with pregnancy outcome data
Postnatal growth deficiency		
Primary analysis between internal cohorts (at 2, 4, 6, and 12 months)	Singleton infants without MCMs who were not born preterm or SGA with postnatal growth deficiency based on weight/length/head circumference among infants with weight/length/head circumference data at the time point	Singleton infants without MCMs who were not born preterm or SGA with weight/length/head circumference data at the time point
Infant developmental delay	-	
Primary analysis between internal cohorts (at 2, 4, 6, and 12 months)	Infants without MCMs who were not born preterm with developmental delay in a particular category among infants with developmental milestone data for the category at the time point	Infants without MCMs who were not born preterm with developmental milestone data for the category at the time point

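### Preterm birth and SGA are restricted to infants without MCMs without fixing the MCM set; read literally, the rule removes preterm infants for a consequence of prematurity

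*Protocol*

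**What the plan says.** **Restriction.** Section 9.7.3.3 states that for preterm birth, SGA, postnatal growth deficiency and developmental delay "prevalence will be calculated among live births/infants without MCMs". The Table 4 internal-cohort rows repeat this. The preterm numerator is "Singleton preterm live births without MCMs among women with pregnancy outcome data" (enrolled before 37 weeks), and the denominator carries the same limit.

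**What counts as an MCM.** Section 9.3.4.1 lists a group of MCMs regarded as unrelated to medication. The group covers chromosomal abnormalities, genetic syndromes, positional effects and "prematurity-related conditions in infants born at < 36 gestational weeks". The examples of the last kind are patent ductus arteriosus, patent foramen ovale, inguinal hernia and undescended testes. These conditions "will not be considered MCMs in the statistical analyses comparing MCM prevalence between the internal cohorts". They are counted for the MACDP and EUROCAT comparisons.

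**Qualifiers in Table 4.** Each MCM row says whether the medication-unrelated group is left out or included. The preterm, SGA, growth and developmental rows say neither.

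**Related rules.** Preterm means below 37 weeks (Section 9.3.4.7). Growth deficiency excludes infants born preterm or SGA, and developmental delay excludes infants born preterm (Section 9.7.3.3). Unrestricted crude rates are optional. The preterm and SGA comparisons with Study C4951006 carry no MCM restriction.

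**The concern.** The carve-out in Section 9.3.4.1 is limited to comparisons of MCM prevalence, and a preterm-birth comparison is not one of those. On the literal text, an infant born at 31 weeks with a patent ductus arteriosus is an MCM infant and leaves both the numerator and the denominator of the preterm analysis. The condition is present because the infant is preterm, so the exclusion is conditional on the outcome being measured. SGA is affected too, because its denominator includes preterm singletons.

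Two things are at stake. The preterm prevalence would be understated in both cohorts. And if rimegepant shifted preterm births to earlier gestations, where these conditions would be expected more often, more exposed than unexposed cases would be deleted. In a safety registry that error points toward missing harm.

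**Working it through.** **Inputs from the protocol (Section 9.5.2, Tables 2 and 3).** The preterm reference rate is 8.47%. The plan is stated as: "The full study will aim to prospectively enroll a minimum of 390 women with migraine who were exposed to rimegepant", with the same number unexposed. After 90% live births and 10% loss to follow-up, this "would result in 316 evaluable participants per cohort". On method: "Power calculations were conducted using nQuery and were based on normal approximation, 2-tailed, alpha 0.05". The Table 3 claim is that 390 per cohort "will afford the study >80% power to detect a 2.5-fold increase in all other outcomes except eclampsia, stillbirth, and TOPFA".

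**Reproducing the plan's figures** (pooled normal approximation, two-sided 0.05):

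- 390 × 0.9 × 0.9 = 315.9, stated as 316.
- MCM, 390 per cohort, 3% vs 7.5%: power 80.6%, stated as 80.6%.
- MCM, 316 per cohort, 3% vs 8.1%: power 80.1%, stated as 80%.
- Preterm, 390 per cohort, 8.47% vs 8.47% × 2.5 = 21.175%: power 99.9%, stated as above 99.0%.

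The stated power is not in dispute.

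**Effect of the literal rule on the preterm rate.** Let p be the true preterm rate and r the share of preterm infants removed for a prematurity-related condition. The protocol gives no value for r, so it is assumed and shown as a range. Removed infants leave both numerator and denominator:

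observed rate = p(1 − r) / (1 − pr)

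- r = 10%: 0.0847 × 0.90 / (1 − 0.00847) = 0.07623 / 0.99153 = 7.69%.
- r = 25%: 0.0847 × 0.75 / (1 − 0.021175) = 0.063525 / 0.978825 = 6.49%.

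In counts, 316 × 0.0847 = 26.8 preterm births are expected at the reference rate. About 2.7 of them go at r = 10% and 6.7 at r = 25%.

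**Equal removal in both cohorts, true relative risk 2.0.** Power is at 316 per cohort, reduced by the removals, i.e. 316 × (1 − 0.0847r):

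| r | Observed RR | Power |
|---|---|---|
| 0% | 2.00 | 89.4% |
| 10% | 2.02 | 86.5% |
| 30% | 2.05 | 78.4% |

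The relative risk barely moves. The cost is a lower rate and some power.

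**More removed in the exposed cohort** (assumed r = 25% exposed, 10% unexposed; unexposed rate 7.69% as above):

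- True RR 2.0: exposed 0.1694 × 0.75 / (1 − 0.04235) = 13.27%, so observed RR 1.73.
- True RR 1.5: exposed 0.12705 × 0.75 / (1 − 0.0317625) = 9.84%, so observed RR 1.28.

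At an assumed 30% against 10%, a true RR of 2.0 appears as 1.63, with power 51.5% against 89.4% when nobody is removed.

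**The narrower reading** (the internal-comparison MCM set applied to the infant rows). Infants with prematurity-related conditions before 36 weeks stay in. Two residues remain.

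- The carve-out stops at 36 weeks and preterm runs to 37, so an infant born in week 36 with a listed condition could still be removed.
- Chromosomal and genetic cases stay in the denominators. Suppose they are a share s = 0.2% to 1.0% of infants (assumed) and all have the outcome. With a 10% growth-deficiency rate and true RR 2.5, the observed RR is [0.25(1 − s) + s] / [0.10(1 − s) + s], which is 2.47 at s = 0.2% and 2.36 at s = 1.0%. This is a small dilution.

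**Growth deficiency and developmental delay.** Every infant below 37 weeks is already out of both analyses, so conditions in infants below 36 weeks cannot change either one under any reading.

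**The case against.** The best defence is that the narrower set is what was meant. The affected rows are labelled as analyses between internal cohorts, Section 9.3.4.1 uses the narrow set for internal comparisons of MCM prevalence, and the inclusive set is named only for MACDP and EUROCAT. Under that set the preterm endpoint is essentially intact. Whether a given ductus is confirmed as an MCM also depends on the evaluators' coding. These outcomes are secondary with nominal p-values, unrestricted crude rates are foreseen, and the detail could be left to the SAP.

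Part of this stands. The intended set may well be the narrow one, and the evaluators' coding cannot be seen from here. But the carve-out is worded for MCM prevalence only, and Table 4 qualifies the same term wherever it means the narrow set. The crude rates are optional. The unrestricted C4951006 comparison is with women without migraine, and Section 7.3 reports that migraine itself is associated with preterm birth, so it cannot replace the internal comparison. The protocol fixes these numerators and denominators itself, so this is not a detail it merely left open.

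A reader might infer something stronger: that either reading spoils the preterm, growth and developmental endpoints alike, or that the relative risk is biased in any case. The documents do not support that. The narrow reading leaves only slight dilution, the growth and developmental analyses already exclude preterm infants, and bias in the relative risk needs unequal removal between cohorts. Nor would all of the earliest cases be lost, only those with a confirmed listed condition.

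**Conclusion.** The point holds for preterm birth and, to a lesser extent, SGA. The MCM set behind the restriction is not stated, and its literal meaning excludes infants because of the outcome or a consequence of it. The lower preterm rate (7.7% or 6.5% instead of 8.47%) follows by arithmetic from assumed removal of 10% or 25%. The attenuation of the relative risk (2.0 to 1.73, 1.5 to 1.28) rests on the further assumption that exposed preterm births are earlier, with 25% against 10% removed. The protocol supplies neither share. No stated power figure is wrong, and the primary MCM analysis is not touched. The ambiguity should be closed before the final comparative analysis, so that the set is not chosen with the data in hand.

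**What to change.** In Section 9.7.3.3 and the Table 4 internal-cohort rows for preterm birth and SGA, state that infants whose only finding is a prematurity-related condition (at any gestational age below 37 weeks) or a positional condition are retained. Use the same MCM set in the postnatal growth and developmental-delay rows, and state there whether chromosomal and genetic cases are excluded.

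The cost is wording only. The primary MCM analysis already requires malformations to be sorted into these categories, and evaluators blinded to exposure already review and classify every reported malformation (Section 9.4.4). No new data are needed.

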9.3.4.8. Small for gestational age (SGA)

SGA will be defined as birth weight $<10^{\text{th}}$ percentile for sex and gestational age. For the determination of SGA, the registry will utilize the sex-specific international growth reference standards from the

PFIZER CONFIDENTIAL

International Fetal and Newborn Growth Consortium for the 21st Century (INTERGROWTH-21st) for infants born between 24^{0/7} and 42^{6/7} gestational weeks.^{48,49} The INTERGROWTH-21st standards are the latest-available, global reference standards, representing contemporary information from an international, multiethnic, diverse population, and have been specifically developed for modern research.

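### Table 4 counts internal SGA on weight/length/head circumference, although Section 9.3.4.8 defines SGA on birth weight alone

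*Protocol*

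**What the plan says.** Four places in the Protocol bear on this outcome.

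- **Section 9.3.4.8 (definition):** "SGA will be defined as birth weight" below the 10th percentile for sex and gestational age, using the INTERGROWTH-21st standards. No other measurement is named.
- **Section 9.5.2, Table 3 (planning):** the row reads "SGA* 10.0% >99.0" (per cent), and the footnote gives the basis of the rate as "By Definition".
- **Section 9.7.3.3, Table 4, internal cohorts:** the numerator is "Singleton live births without MCMs who are SGA based on weight/length/head circumference among women with pregnancy outcome data" and the denominator is "Singleton live births without MCMs with weight/length/head circumference data among women with pregnancy outcome data".
- **Section 9.7.3.3, Table 4, comparison with Study C4951006:** the numerator is "Live births who are SGA based on weight among women with pregnancy outcome data".

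Section 9.7.3.3 and Table 4 also remove infants born preterm or SGA from the postnatal growth deficiency denominator, without saying on which measurement SGA is judged there.

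**The concern.** One name covers different outcomes. The external row specifies weight, so the internal row is hard to read as shorthand for weight. An analyst who follows Table 4 would label as SGA some infants of normal birth weight who are short or have a small head. Those infants do not meet the Protocol's own definition.

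Three things are at stake:

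- what the internal relative risk for SGA estimates;
- who enters its denominator, since an infant with a birth weight but no recorded length or head circumference may drop out;
- which infants are removed from the postnatal growth deficiency analysis.

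Section 7.2 gives the outcome some specific interest: reduced fetal body weight was seen in rats, though only at very high exposures that were also toxic to the mothers. While the slash is undefined, the reading could also be chosen after the data are seen.

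**Working it through.** **1. The Protocol's own figure.** Inputs from Section 9.5.2 and Table 3: 390 per cohort, reference rate 10%, relative risk (RR) 2.5 (so 25%), two-sided 0.05, normal approximation. With the pooled-variance formula

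z = [ |p2 − p1|√n − 1.96√(2p̄(1 − p̄)) ] / √( p1(1 − p1) + p2(1 − p2) )

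and p̄ = 0.175, z = (0.15 × 19.75 − 1.96 × 0.537) / 0.527 = 3.62, so power is 99.99%. At the 316 evaluable participants it is 99.9%. Both agree with the stated figure of more than 99.0%. The same formula returns 80.6% for major congenital malformations (MCMs), as stated in Table 2.

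**2. What the slash could mean.**

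- *One analysis per measure:* each measure is cut at its own 10th percentile, so 10% holds for each. Low length or small head is still reported as SGA, against Section 9.3.4.8.
- *Any one of three:* the rate exceeds 10% unless the measures overlap completely. It cannot exceed 3 × 10% = 30%.

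**3. Size under the any-of-three reading.** The Protocol gives no correlations between the measures, so a common correlation is assumed in a trivariate normal model. Under independence the reference rate is 1 − 0.9³ = 27.1%. If only the weight criterion doubles, from 10% to 20%, the composite becomes 1 − 0.8 × 0.9 × 0.9 = 35.2%, and RR = 35.2 / 27.1 = 1.30. The share of composite cases not meeting the birth-weight definition is 1 − 10/27.1 = 63%.

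| Assumed correlation | Composite reference rate | Cases not low birth weight | Rate if only low weight doubles | Composite RR | Power, N = 390 | Power, N = 316 |
|---|---|---|---|---|---|---|
| 0 | 27.1% | 63% | 35.2% | 1.30 | 69% | 60% |
| 0.5 | 21.8% | 54% | 28.7% | 1.31 | 59% | 51% |
| 0.7 | 19.0% | 47% | 25.4% | 1.34 | 59% | 50% |
| 0.9 | 15.0% | 33% | 21.5% | 1.44 | 66% | 57% |

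For comparison, weight-only SGA rising from 10% to 20% has 98% power at N = 390 and 94% at N = 316.

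The table lets newly low-weight infants overlap with those already counted on length or head. With no such overlap and a composite rate of 20%, RR = (20 + 10) / 20 = 1.5, with power of about 90% at N = 390.

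**4. Effect on Table 3.** A 2.5-fold increase in the composite itself has power above 99.9% at every correlation tried. A 2.5-fold increase confined to low birth weight would appear as a composite RR of about 1.45 to 1.72, with power of 91% to 96% at N = 390.

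**The case against.** The strongest reply is that the slash probably means three parallel analyses. The cited growth standard covers weight, length and head circumference separately. The neighbouring developmental delay row is analysed category by category. Table 3 also gives postnatal growth deficiency, which carries the same slash in Table 4, a rate of 10% by definition. On that reading there is no composite and no dilution, and the 10% rate holds for each measure. This is plausible but not settled. The developmental delay row states its per-category basis and the SGA row does not, while Section 9.3.4.9 joins the same three measures with an explicit "or" for postnatal growth deficiency. Even if the reply is right, two of the three analyses would carry the SGA label against Section 9.3.4.8.

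A reader might infer that the 10% planning rate has failed or that the study is underpowered for SGA. The Protocol does not support that: the rate fails only if a composite is meant, and Table 3's conclusion for a 2.5-fold increase in the outcome survives either way.

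A reader might also infer that this wording is what makes the internal and external SGA rates incomparable. Section 9.7.3.3 says that external comparisons follow the comparator's conventions, and the two rows already differ in the restriction to singletons and the exclusion of MCMs. They would still differ after the fix.

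On the postnatal exclusion, it is fair to say that an unqualified reference to SGA should default to Section 9.3.4.8. Table 4 applies a different meaning in the row above, so this needs to be stated.

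The SAP, which is not at hand, could explain the slash. It would still leave two conflicting statements in the Protocol.

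**Conclusion.** The contradiction holds. Section 9.3.4.8 and the external row use birth weight; the internal row adds length and head circumference to both numerator and denominator. This is certain from the text and does not depend on how the slash is read.

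The numerical consequences are conditional on a composite and on assumed correlations. In that case the reference rate is about 15% to 27%, and a doubling confined to low birth weight appears as an RR of about 1.3 to 1.4 (1.5 without overlap at a 20% composite rate). Confining the effect to weight is the unfavourable case. An effect that also reduced length or head circumference would be diluted less.

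The primary outcome and the sample size are untouched. SGA is secondary, and Section 9.7 treats its p-values as nominal. Severity is moderate to minor: it should be corrected before the final comparative analysis, but it does not threaten the study's main conclusion.

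**What to change.** Make three wording changes in Table 4:

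1. Define internal SGA as birth weight below the 10th percentile (INTERGROWTH-21st), among singleton live births without MCMs who have birth weight, sex and gestational age data.
2. Report length and head circumference below the 10th percentile as separately named outcomes, each with its own denominator.
3. State that the postnatal growth deficiency exclusion uses birth-weight SGA.

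If the sponsor does want an any-of-three composite, it should have its own name, an explicit rule and its own reference rate.

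The cost is a text amendment. Section 9.4.1.2 already collects sex, birth weight, length, head circumference and gestational age at outcome, so no new data are needed and the sample size does not change.
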